9.9.4 Discharge from hospital (length of stay)

Discharge from hospital will be analysed using Cox proportional hazard models to test the hypothesis that there is no difference in this between the control and intervention groups.

Kaplan-Meier survival curves, median length of hospital stay, and the log-rank test result will also be presented. Both adjusted (age, sex, baseline troponin level, hypertension, diabetes, heart failure) and unadjusted Hazard Ratios (HR) and their 95% Confidence Interval (CI) will be presented. The adjusted results taken as primary. For Cox regression models the proportionality assumption will be assessed graphically (using diagnostic plots). If the assumption does not meet the median difference and the result of log rank test will be presented.

Both the length of stay from admission and length of stay from randomisation will be presented.

9.9.5 Binary outcomes (need for invasive ventilatory support, mechanical circulatory support, renal replacement therapy, ECMO)

Binary outcomes including:

- need for non-invasive ventilatory support
- need for invasive ventilatory support
- need for mechanical circulatory support
- need for renal replacement therapy

will be compared between the arms using logistic regression adjusting for the stratification factors and for variables included in the primary model. The aim of this model is to test if there is a significant difference in these binary outcomes and to estimate the magnitude of the difference. Results will be presented as odds ratios compared to the control group and their 95% confidence intervals.

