6.6 Sample size

Estimating the required sample size for the trial is challenging as a good estimate for the mortality rate with standard treatment strategies for ACS in the UK will not be known for a while. There are further challenges with shifting clinical practice and the government recommendations which could alter the 'at risk' population and standard treatment given. As a result we have chosen to size the trial in the first instance based on the best available data we have and use recognised parameters within this calculation (90% power and 5% significance level) (6.6.1). However, given the great uncertainties and potential shifts we do not aim to restrict this trial to a narrow hypothesis-testing framework. The aim of this study is to estimate the effect of the treatment strategy effect with good precision. The power calculation included in 6.6.1 will ensure we have a good prospect of this. This means interpretation will not be restricted using a single binary threshold of 5% significance, but the p-value will be interpreted on the continuous scale as strength against the null hypothesis. This will be presentation of the treatment effect estimate and 95% confidence intervals. The DMC will monitor the assumed all-cause mortality rate and will advise on extending the trial if they deem greater precision will result in better information for decision-making.

A Bayesian analysis will also be undertaken on the primary outcome to further encourage intelligent interpretation of study results. This will allow us to report on the posterior probability for 30-day all-cause mortality being superior in the ACS treatment strategy arm compared to standard treatment approach. In addition, a Bayesian analysis of the longitudinal ordinal outcomes over the 30 day follow-up period.

6.6.1 30-day all-cause mortality

Assuming 25% mortality in the control arm (Wuhan retrospective data of COVID-19 patients requiring in-hospital treatment), 3000 patients will provide 90% power at the 5% significant level to detect a 20% reduction in mortality. Inflating the number to account for missing outcome data in 2%, we plan to recruit and randomize 3062 participants.

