9.2 Analysis principles

All the analysis will be conducted on an intention-to-treat basis unless otherwise specified. Only participants withdrawing from data collection will be excluded from the analysis. All hypothesis tests will be two-sided. No correction for multiple testing for secondary outcomes will be made but all secondary outcomes will be reported for transparency of the number of tests undertaken. All analyses will be adjusted for randomization minimisation variables and other names variables used in the primary analysis (pre-specified in the SAP) unless otherwise stated.

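### SAP 9.9.4 analyses time to discharge with no rule for in-hospital death, so the Kaplan-Meier curves and median can misstate discharge and the hazard ratio is not fully defined

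*SAP*

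**What the plan says.** Time to discharge is a non-key secondary outcome. Section 9.9.4 sets the model: "Discharge from hospital will be analysed using Cox proportional hazard models to test the hypothesis that there is no difference". It adds: "Kaplan-Meier survival curves, median length of hospital stay, and the log-rank test result will also be presented". If proportional hazards fails on the diagnostic plots, the median difference and the log-rank result are reported instead. Stay is presented both from randomisation and from admission.

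The section does not say whether an in-hospital death is censored at death, counted as the end of the stay, or kept as never discharged. It names no horizon. Section 9.3.1 deals only with missing mortality data. No competing-risk method or cumulative incidence function appears anywhere in the SAP.

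The size of the competing event comes from section 6.6.1: "Assuming 25% mortality in the control arm", and "3000 patients will provide 90% power at the 5% significant level to detect a 20% reduction in mortality".

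Death is a state in one other analysis, the ordinal scale of sections 8.4 and 9.9.1, which ranks it worst. Section 4 makes the SAP govern over the protocol on planned analyses, so the rule belongs here.

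**The concern.** A patient who dies in hospital can never be discharged. Censoring at death treats that patient as someone who would later have gone home at the same rate as those still on the ward. The Kaplan-Meier complement then no longer estimates the proportion discharged, and its median no longer estimates the time by which half have gone home. The fallback for non-proportional hazards uses the same median and a log-rank test with the same undefined handling of deaths, so it gives no protection.

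The trial is designed around an effect on death, so the competing event is expected to be unequal between arms. Patients whose deaths are averted are likely to be sicker and slower to leave. Depending on how deaths are coded, their longer stays can make the arm with fewer deaths look slower, no different or faster. If the coding is chosen after the data are seen, that choice can decide the sign of the estimate.

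**Working it through.** **1. The plan's own figure.** Inputs from 6.6.1: 25% control mortality, a 20% relative reduction (so 20%), 90% power and 5% significance, two-sided by 9.2.

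n per arm = [1.960·√(2·0.225·0.775) + 1.282·√(0.25·0.75 + 0.20·0.80)]² / 0.05² = 1464, or 2928 in total. With continuity correction it is 1504 per arm, 3008 in total. Both are within 3% of 3000, and 1500 per arm gives power 0.907. Then 3000/0.98 = 3061.2, which agrees with 3062. The design mortality of 25% against 20% is therefore used below.

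**2. Size of the overstatement.** The SAP gives no discharge rates, so the daily discharge hazard λ is an assumption, constant and equal in both arms. The death hazard μ is solved so that 30-day mortality is 25% (control) or 20% (treated).

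- Died by day 30: μ/(λ+μ)·(1 − e^(−30(λ+μ)))
- Truly discharged by day 30: λ/(λ+μ)·(1 − e^(−30(λ+μ)))
- One minus Kaplan-Meier, deaths censored: 1 − e^(−30λ)

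Example, λ = 0.08, control: μ = 0.0281, so discharged = 0.08/0.1081 × (1 − e^(−3.243)) = 0.711. Kaplan-Meier gives 1 − e^(−2.4) = 0.909.

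| λ | Truly discharged, control / treated | Kaplan-Meier, both arms | Overstatement (points) | Kaplan-Meier median (days) | Cumulative-incidence median, control / treated (days) |
|---|---|---|---|---|---|
| 0.05 | 62.7% / 65.9% | 77.7% | 15.0 / 11.8 | 13.9 | 17.2 / 16.2 |
| 0.08 | 71.1% / 75.2% | 90.9% | 19.8 / 15.7 | 8.7 | 10.4 / 9.9 |
| 0.12 | 74.2% / 78.9% | 97.3% | 23.1 / 18.4 | 5.8 | 6.9 / 6.6 |

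Kaplan-Meier is identical in the two arms, although 3 to 5 points more treated patients go home. The overstatement cannot exceed the arm's mortality, because censoring only reallocates the patients who died. It would shrink if mortality were below 25%.

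**3. A scenario in which the sign changes.** Assumed: 35% severe patients (discharge 0.03 per day, death 0.055 per day) and 65% mild (0.15 and 0.006). Treatment multiplies only the death hazard, by 0.72. Recomputed in closed form, with hazard ratios by simulation:

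| | Control | Treated |
|---|---|---|
| 30-day mortality | 23.4% | 19.2% |
| Truly discharged by day 30 | 73.3% | 75.8% |
| One minus Kaplan-Meier | 90.3% | 88.8% |
| Cumulative-incidence median (days) | 7.8 | 7.6 |
| Kaplan-Meier median (days) | 6.9 | 7.0 |

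The discharge hazard ratio is about 0.97 with deaths censored and 1.05 with deaths kept in the risk set to day 30. The reversal arises because treatment keeps more severe, slow-to-leave patients in the risk set.

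**4. How far the direction depends on assumptions.** A second simulation (30,000 per arm) assumed that 75% survive with a mean stay of 8 days and that treatment averts 5 points of deaths. Only the fate of the averted deaths varies. Hazard ratios below 1 look slower:

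| Averted deaths | Censored at death | Death as end of stay | Kept to day 30 |
|---|---|---|---|
| Still in hospital at day 30 | 0.93 | 0.87 | 1.01 |
| Home on days 15 to 30 | 0.98 | 0.92 | 1.08 |
| Home after a mean of 20 days | 1.01 | 0.95 | 1.08 |
| Home as fast as other survivors | 1.09 | 1.01 | 1.14 |

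**5. Visibility at trial size.** In the step 3 scenario, discharges = 1500 × (0.733 + 0.758) ≈ 2236, and SE(log HR) ≈ 2/√2236 = 0.042. Then z = ln(0.97)/0.042 ≈ −0.7 and z = ln(1.05)/0.042 ≈ 1.15. Neither would be distinguishable from 1. Larger shifts occur in step 4 if death counts as the end of stay: expected z is about −3.9 in the first row and −2.3 in the second.

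**The case against.** The strongest reply is that 9.9.4 prescribes no wrong handling. It never says deaths are censored, and keeping them undischarged to day 30 is compatible with its Cox wording. A Cox model that does censor at death is a valid comparison of cause-specific discharge hazards. The hazard-ratio shift in step 3 is small against its standard error, and step 4 includes a row where censoring favours treatment. Mortality is the primary outcome and will be read beside length of stay. The key secondary ordinal analysis already combines death, advanced care and discharge.

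Most of this stands, and it limits the point. It does not rescue the Kaplan-Meier curves and median as descriptions of discharge if deaths are censored, nor does it tell the analyst which estimand the Cox model targets.

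Three stronger readings are tempting but unsupported:

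- **That the covariate list breaks 9.2.** Section 9.2 says "All analyses will be adjusted for randomization minimisation variables", and the 9.9.4 list omits coronary disease and site. But the same sentence of 9.2 exempts analyses that specify something different, and 9.9.4 gives its own list. Adding the two factors may gain precision; leaving them out is not a contradiction.
- **That 9.9.5 counts support already in place at randomisation as an event.** The SAP does not say so, and the definition of need for support may sit in the protocol or case report form.
- **That 9.9.5 must become a composite.** The support outcomes "will be compared between the arms using logistic regression adjusting for the stratification factors and for variables included in the primary model". Death without support is not addressed there, so these results need to be read with mortality. Odds ratios of 1.07 to 1.59 against a life-saving arm can be produced, but only by assuming that the averted deaths would have been unsupported and that 25% to 100% of those patients then survive on support. The SAP has no data on this. A composite would also change the endpoint and overlap the primary outcome and the ordinal scale.

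**Conclusion.** The point holds for 9.9.4 and should be fixed. With deaths censored, the planned curves would overstate discharge by day 30 by about 12 to 23 points and shorten the median by about 1 to 3 days. This assumes constant discharge hazards of 0.05 to 0.12 per day and the SAP's own 25% against 20% mortality. The contrast between arms can be hidden or, in some scenarios, change sign with the handling of deaths.

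A reader might infer that the plan will make a life-saving treatment look harmful. The documents do not support that: the rule is unstated rather than wrong, the direction depends on what happens to patients whose deaths are averted, and the step 3 shift would be lost in sampling error. The outcome is a non-key secondary, and the primary analysis is untouched.

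**What to change.** In 9.9.4:

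- Define the outcome as time to discharge alive within 30 days of randomisation, and apply the same rule for deaths to the version measured from admission.
- Keep patients who die in hospital as not discharged to day 30, by a Fine-Gray model or a Cox model with deaths censored at day 30 rather than at death.
- Replace the Kaplan-Meier curves with cumulative incidence of live discharge by arm, and take the median from it. Make the same change in the fallback for non-proportional hazards, with the log-rank test computed under the same rule for deaths.
- Optionally, show the cause-specific hazard ratio alongside. The ratio with deaths kept in the risk set mixes effects on discharge and on death, and this helps separate them.
- Optionally, add coronary disease and site to the covariates for precision.

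In 9.9.5, keep the planned outcomes and add support or death by day 30 as a supplementary tabulation only.

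The cost is SAP wording and recoding of discharge and death dates that are already collected. No new data or extra patients are needed. It should be settled before outcome data are seen by arm.

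### If proportional hazards fails for time to discharge, the fallback reports a median difference with no confidence interval beside a log-rank p-value that does not test it

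*SAP*

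**What the plan says.** Section 9.9.4 sets the main analysis: "Discharge from hospital will be analysed using Cox proportional hazard models to test the hypothesis that there is no difference in this". Adjusted and unadjusted hazard ratios are both reported with 95% CIs, and for their ranking the section says "The adjusted results taken as primary". The adjustment covariates are age, sex, baseline troponin, hypertension, diabetes and heart failure.

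Whether or not the model fits, "Kaplan-Meier survival curves, median length of hospital stay, and the log-rank test result will also be presented".

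The model check is visual, with no stated criterion: "the proportionality assumption will be assessed graphically (using diagnostic plots". If it fails: "If the assumption does not meet the median difference and the result of log rank test will be presented".

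Section 9.2 adds that "All hypothesis tests will be two-sided". The SAP gives no expected discharge rate, median stay or target difference for this outcome.

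**The concern.** The median in each arm and the log-rank result are already promised in every case. The fallback therefore adds only the subtraction of one median from the other. That difference becomes the effect measure just when the hazard ratio stops being a good summary, and it comes without an interval.

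The p-value printed next to it answers another question. Log-rank is the score test of the Cox model with treatment as the only term. It adds up differences in hazard over the whole follow-up and is most powerful when the hazard ratio is constant. When the ratio crosses 1, early and late differences offset each other. The reverse can happen too: equal medians beside a very small p-value. In either case a reader has nothing with which to judge the precision of the estimate.

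**Working it through.** **1. Arm size, from the plan's own figure.** Section 6.6.1 says "3000 patients will provide 90% power at the 5% significant level to detect a 20% reduction in mortality", with "Assuming 25% mortality in the control arm", so the rates are 25% v 20%.

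n per arm = [1.96·√(2·0.225·0.775) + 1.2816·√(0.25·0.75 + 0.20·0.80)]² / 0.05² = 1,464, or 2,928 in total (3,008 with continuity correction). Power at 1,500 per arm is 0.907, and 3,000/0.98 = 3,062. The figure reproduces. It concerns mortality only and is used here just to take 1,500 per arm.

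**2. Log-rank and the Cox score test.** On one simulated data set the Cox score chi-square, with treatment alone and β = 0, was 0.84423. The log-rank chi-square was also 0.84423. The identity holds for the unadjusted model only.

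**3. Assumed discharge pattern.** Control hazard 0.10/day, follow-up to day 30, deaths left out. Intervention hazard ratio 1.2 to day 7, then 0.8.

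- Control median: ln 2/0.10 = 6.93 days.
- Intervention median: ln 2/0.12 = 5.78 days.
- Difference: 1.16 days.

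**4. Log-rank power.** With equal arms, the expected numerator is about ¼·Σ D·ln(HR) and the variance about ¼·ΣD, where D is the number of discharges in each period.

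- To day 7: D = 1,500·[(1 − e^−0.70) + (1 − e^−0.84)] = 1,608.
- Days 7 to 30: D = 1,500·[(e^−0.70 − e^−3.00) + (e^−0.84 − e^−2.68)] = 1,215.
- Numerator: ¼·(1,608·0.1823 − 1,215·0.2231) = 73.3 − 67.8 = 5.5.
- SD: √(¼·2,823) = 26.6.
- Expected z: 0.21, so power is about 5.5%. Simulation gives about 6%.

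**5. Power of a test of the median difference.** The standard error of each median is about 1/(√n·h), with h the hazard at the median.

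- SE of the difference: √[(1/(38.7·0.10))² + (1/(38.7·0.12))²] = 0.336.
- Expected z: 1.16/0.336 = 3.44, so power is about 93%. Simulation gives about 92%.

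**6. Other patterns (simulated, 1,500 per arm).**

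| Hazard ratio, early then late | Change at day | Median difference | Log-rank | Median test |
|---|---|---|---|---|
| 1.2 then 0.8 | 7 | 1.2 days shorter | about 6% | about 92% |
| 1.2 then 0.9 | 7 | 1.2 days shorter | 34% | 91–94% |
| 1.2 then 1.0 | 7 | 1.2 days shorter | 77–78% | 91–94% |
| 1.2 then 1.1 | 7 | 1.2 days shorter | 97% | 91–94% |
| 0.85 then 1.2 | 7 | 0.9 days longer | 5–6% | 75% |
| 1.0 then 1.15 | 3 | 0.5 days shorter | 76–78% | 31–33% |

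Under no effect both tests reject in about 3–5% of runs.

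**7. A second set of hazards.** Control 0.08/day (median 8.66). Intervention 0.104/day to day 8, then 0.056 (median 6.66). The true difference is 2.0 days. At 1,500 per arm log-rank rejects in 5.5% of runs and the median test in 99.7%. With a late hazard of 0.040 instead, log-rank rejects in 81%. In the reverse case, with both medians at 8.66 days and the hazard halved after day 9, log-rank rejects in 78% of runs at 250 per arm and 100% at 1,500.

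**8. Restricted mean to day 30.** In the pattern of step 3 it is (1 − e^−3)/0.10 = 9.50 days in control. In the intervention arm it is (1 − e^−0.84)/0.12 + (e^−0.84 − e^−2.68)/0.08 = 9.28 days. The difference is only about 0.2 days. Its simulated power was 12% and 6% in the two crossing patterns with day-7 changes (1.2 then 0.8; 0.85 then 1.2). It describes the whole curve but does not recover the lost power.

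**The case against.** The best defence is that nothing here is invalid. The hypothesis in section 9.9.4 concerns discharge as a whole, and log-rank tests equality of the discharge curves with correct size whether or not hazards are proportional. An overall p-value beside a descriptive effect measure is a common form of report. The lowest power figures need an early effect almost exactly offset by a late one, with the change placed close to the control median. With milder or no reversal log-rank does well, and for a delayed effect it clearly beats the median test. All of this stands, and it is why log-rank should be kept.

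Some stronger readings are tempting but not supported:

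- A reader might infer that the SAP offers log-rank as the test of the median difference. It only lists the two together.
- A reader might infer that log-rank repeats the primary Cox analysis. The primary model is adjusted, and the identity holds only for the unadjusted one.
- A reader might infer that the adjusted hazard ratio is withdrawn when the assumption fails. The sentence promising hazard ratios is unconditional, and the fallback does not cancel it. It simply names no adjusted quantity of its own.
- A reader might infer that a real difference would be reported as none. The median difference and the curves are still shown, so crossing would be visible. Sections 6.6 and 9.11 also disclaim a single p-value threshold, although they speak of the sample-size framework and the interim analysis rather than this outcome.

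What the defence does not answer is the missing interval.

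**Conclusion.** The point holds in a limited form. After a failed check the fallback estimate has no stated precision, and the p-value beside it can point elsewhere, in either direction. Under crossing hazards the gap can be about 6% against 92% at 1,500 per arm. Without crossing it is small or reversed.

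The sizes rest on assumed discharge hazards, no deaths and 1,500 per arm. With 300 per arm the median test itself falls to 33% and 21% in the two crossing patterns with day-7 changes, against about 6% for log-rank. In-hospital death prevents discharge, and the SAP assumes 25% control mortality, so the handling of deaths would shift the median, the restricted mean and log-rank alike. The figures show that disagreement is possible; they do not forecast it.

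The point is minor: it is a conditional analysis of a secondary outcome below the key one, and the primary result is untouched.

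**What to change.** Replace the fallback sentence in section 9.9.4 with:

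> If proportional hazards is not supported, the effect will be the difference in median time to discharge with its own 95% CI (bootstrap or censored quantile regression, adjusted for the covariates listed in this section), supplemented by the difference in restricted mean time to discharge to day 30 with 95% CI. The log-rank p-value will be reported as an overall test of equal discharge curves, not as the test of the median difference.

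The interval for the median difference is the essential part; the restricted mean is only a supplement. Whatever rule is used for in-hospital deaths should be the same for all three quantities.

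The cost is one sentence and a little programming, with no new data. The median comparison is less powerful than log-rank in some non-crossing patterns, so log-rank stays in the report.

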9.10 Safety analysis

9.10.1 Bleeding Academic Research Consortium (BARC) bleed event at 30 days

The BARC bleed event at 30-days will be analysis using a proportional odds model, including the same baseline variables as the primary model. The aim of this model is to test if there is a significant difference in these ordinal outcomes and to estimate the magnitude of the difference. Results will be presented as odds ratios compared to the control group and their 95% confidence intervals.

9.10.2 Bleeding Academic Research Consortium (BARC) grade 3 to 5 bleed event at 30 days

This will be calculated in a similar way to the primary outcome.

9.11 Interim analysis

The interim analysis will be performed after a minimum of 170 participants have been recruited and have a minimum of 7 days follow-up. The DMC will be responsible for reviewing all the data and advising on whether the trial should continue.

The following outcomes will be summarized by arm and compared between arm by calculating odds ratios, incidence rate ratios for count outcomes, or differences in mean. Safety summary statistics and between arm comparisons will be tabulated. Differences will be presented with 95% confidence intervals and p values, but the p-values will be interpreted in terms of strength of evidence using the continuous scale and not based on a binary threshold (e.g. 0.05).

- Bleeding Academic Research Consortium (BARC) bleed at 30-days post randomization
- peak troponin within 7- and 30-days post randomization
- recruitment rate
- proportion of missing data for troponin and mortality where due.
- Control event rates

A Kaplan Meier estimate for survival will also be presented with 95% CI around the curves

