5.3 Primary objective of internal pilot (Phase 1)

In order to ensure the study is a worthwhile undertaking and is safe we have included an internal pilot to assess the potential for bleeding harms.

The SAP was amended (version 2) to remove the assessment of efficacy from the objectives at the interim analysis. This change was made based on a blinded assessment of data completeness by the trial steering committee after recommendations were made by the data monitoring committee. Similarly, the effect on troponin and d-dimer were from the objectives of the interim analysis.

- To evaluate the harm profile of the combined treatment with a focus on bleeding outcomes.
- To assess the recruitment process and data collection quality.
- To check the control event rate included in the sample size calculation for Phase 2.
- To monitor adherence to the randomised arm (assessing the potential for contamination)

Internal pilot outcomes:

- Bleeding Academic Research Consortium (BARC) bleed at 30-days post randomization
- recruitment rate
- proportion of missing data for key outcomes
- control event rates

6 Design

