6.1 Study design

Parallel two arm randomized, single blind controlled trial with internal pilot.

C-19-ACS is a study determine if Acute Coronary Syndrome (ACS) is a major cause of mortality in patients with Novel Coronavirus 2 Related Disease (COVID-19) in patients. The study will randomize patients with confirmed COVID-19 in hospital to a 28-day course of standard ACS treatment to determine if the established ACS therapy has an impact on cardiovascular-outcomes.

The trial will include two phases: phase 1 and phase 2. Phase 1 will act as an integrated internal pilot with a close evaluation of safety, assessment of recruitment, contamination and quality of data collection. In phase 1, recruitment will include a minimum 170 patients of the total 3062

needed for the trial. The phase 1 analysis will occur after approximately 170 participants have 7 days follow-up information available. The result will be reviewed by an independent Data Monitoring Committee (DMC) who will make a recommendation to continue or halt the trial based on safety, or feasibility/quality issues. The DMC will also monitor the mortality event rate throughout the trial with the potential to recommend an increase to the sample size if it is assessed that increasing the precision of the treatment effect estimate will likely help inform subsequent policy treatment decisions through strengthening of evidence.

If there are no concerns at the end of phase I assessment, the trial will continue onto phase 2 in which a further approximately 30 sites will be recruited.

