6.2.2 Duration of study medications

The study medications will be continued for 28 days with the patients provided with the remaining medications at discharge from hospital.

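### The interim look is triggered at 7 days but reports 30-day bleeding and a 30-day control mortality rate, with no rule for patients who have not reached day 30

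*SAP*

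**What the plan says.** The trigger for the phase 1 look is given twice. SAP 6.1 has "The phase 1 analysis will occur after approximately 170 participants have 7 days follow-up information available", and SAP 9.11 has "The interim analysis will be performed after a minimum of 170 participants have been recruited and have a minimum of 7 days follow-up".

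SAP 5.3 and 9.11 both list this outcome for the look: "Bleeding Academic Research Consortium (BARC) bleed at 30-days post randomization". Two of the pilot objectives in 5.3 are "To evaluate the harm profile of the combined treatment with a focus on bleeding outcomes" and "To check the control event rate included in the sample size calculation for Phase 2". The rate in that calculation is 30-day mortality (6.6.1): "Assuming 25% mortality in the control arm". On treatment length, 6.2.2 states: "The study medications will be continued for 28 days".

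On method, 9.11 compares arms by odds ratios, incidence rate ratios for counts, or mean differences, and adds a Kaplan-Meier estimate for survival. SAP 9.7 brings in the 9.8 mortality analysis and the 9.10 safety analyses. In 9.10, BARC bleeding has a proportional odds model, and BARC grade 3 to 5 is handled like the primary outcome. SAP 9.3.1 restricts the mortality analysis to participants whose 30-day status is known. SAP 7.2 promises a further exposure-based analysis of bleeding but does not define it or tie it to the interim.

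**The concern.** A patient at the minimum follow-up has had 7 of 28 treatment days, a quarter of the course, yet is to contribute to a 30-day outcome. The SAP does not say whether such a patient counts as event-free, is censored, or is left out. SAP 9.11 allows for outcomes not yet due only when it counts missing troponin and mortality data.

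Bleeding is the more exposed of the two outcomes. It is the focus of the pilot and feeds the DMC's recommendation to continue or halt before about 30 more sites join (6.1). Neither an odds ratio nor a proportional odds model handles incomplete follow-up. The follow-up scheme adds to the problem. SAP 5.2 reports that many patients went home within 1 or 2 days of randomization, and 6.7.1 schedules no contact after discharge before the day-30 call. A discharged patient who has not reached that call has had no scheduled check for bleeding at home, so recording no bleed is an assumption and not an observation.

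For mortality, 6.1 lets the DMC recommend a larger trial in the light of the event rate. A rate distorted by immature follow-up is a poor basis for that advice.

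**Working it through.** **1. The plan's own sample size.** SAP 6.6.1 states: "3000 patients will provide 90% power at the 5% significant level to detect a 20% reduction in mortality". With 25% against 20%, two-sided 5% and 90% power:

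n per arm = [1.960·√(2·0.225·0.775) + 1.282·√(0.25·0.75 + 0.20·0.80)]² / 0.05² = 1464, or 2928 in total. With continuity correction it is 1504 per arm, 3008 in total. Power at 1500 per arm is 0.907. Then 3000/0.98 = 3061.2, rounded up to 3062. The stated figures are reproduced and are not in question.

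**2. Model for the interim.** Fix the true 30-day risk p and set F(t) = 1 − exp[−H·(t/30)^k], with H = −ln(1 − p). Use k = 1 (constant hazard) and k = 0.5 (early-weighted hazard). Let the 170 patients accrue uniformly over A days, with the last one at day 7, so follow-up runs evenly from 7 to 7 + A days. For mortality p = 25% (6.6.1). For bleeding p = 5% is assumed. The values of k and A are also assumptions, because the SAP gives none of the three.

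**3. Worked case: p = 25%, k = 1, A = 30.** H = 0.2877, or 0.00959 per day.
- Share past day 30: 7/30 = 0.233, about 40 of 170.
- Mean F between days 7 and 30: 1 − (0.9351 − 0.75)/(23·0.00959) = 0.161.
- Everyone counted: (23/30)·0.161 + (7/30)·0.25 = 0.182.
- Early deaths kept, survivors short of day 30 dropped: 0.182/(0.182 + 0.233·0.75) = 0.51.

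**4. Results.** Each range covers k = 1 and k = 0.5.

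| Assumed accrual A | Patients at day 30 | True 25% mortality, everyone counted | True 25% mortality, known 30-day status only | Bleeding, everyone counted, as share of truth |
|---|---|---|---|---|
| 30 days | about 40 | 18.2-21.0% | 51-55% | 71-83% |
| 60 days | about 105 | 21.6-23.0% | 32-33% | 86-91% |
| 90 days | about 127 | 22.7-23.7% | 29-30% | 90-94% |

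**5. What a low reading would do to the sample size.** Keep the 20% relative reduction and use the uncorrected formula of step 1. A control rate of 21.0% needs 1824 per arm (1824/1464 = 1.25), and 18.2% needs about 2170 (1.48). So the 30-day accrual case would suggest a trial 25% to 48% larger when the true rate is still 25%.

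**6. Precision.** With all 170 mature there are about 85 controls. SE = √(0.25·0.75/85) = 4.7 points, and the 95% interval is about 16% to 34%. If only patients past day 30 are used and A = 30, there are about 20 controls. SE = √(0.1875/20) = 9.7 points, so the interval is about ±19 points.

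**The case against.** A reader might infer that both figures are bound to come out far too low. If everyone stood at exactly day 7, a true 25% would read as 1 − 0.75^(7/30) = 6.5% under constant hazard, or 13.0% if early-weighted. The documents do not support that as the expected result. Seven days is a minimum, and earlier recruits will have longer follow-up. The table shows a far smaller shortfall once accrual is spread out.

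The direction is not fixed either. The known-status rule of 9.3.1, if carried into the interim through 9.7 and 9.8, pushes mortality up. Whether it is carried in is itself unclear, since 5.3 says efficacy was removed from the interim objectives.

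Other points in the plan's favour also stand:
- A Kaplan-Meier estimate at day 30 is not biased low if censoring is non-informative. However, 9.11 lists control event rates as a separate item and does not say they come from the curve, and the event table in 9.13.3 stops at day 14.
- SAP 7.2 provides for an exposure-based bleeding analysis, though without content.
- Both arms are cut on the same date under 1:1 allocation. Truncation therefore costs events and precision, but does not by itself bias the between-arm ratio unless the effect on bleeding changes over time.
- The DMC goes on monitoring mortality after the pilot (6.1), and no sample-size decision is tied to this look.

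It would also be wrong to infer a risk of stopping for futility. The SAP has no futility rule, and 6.1 limits the pilot recommendation to safety and feasibility or quality.

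**Conclusion.** The mismatch is real and lies in the text: a 7-day trigger, 30-day outcomes, and no rule to connect them. Followed literally, the plan distorts the absolute bleeding risk shown to the DMC and can distort the control mortality rate in either direction.

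With everyone counted, the understatement is roughly 6% to 29% of the true bleeding risk across the assumed accrual periods. A true 25% mortality reads between about 18% and 24%. Restricting to known 30-day status instead reads 29% to 55%. These sizes rest on the assumed accrual periods, hazard shapes and 5% bleeding risk. What does not depend on them is that the SAP allows readings this far apart.

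Bleeding is the stronger part of the point, because it has no specified time-to-event method and no scheduled ascertainment between discharge and day 30. For mortality, the remedy is largely in the plan already and has only to be tied to the control rate. The final analysis and the stated sample size are unaffected.

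**What to change.** Keep the 7-day safety look and amend 5.3, 9.7 and 9.11 as follows.

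- **Bleeding.** In place of the 30-day odds ratio, report by arm events per observed person-day and cumulative incidence with death as a competing event. Censor each patient at the last date on which bleeding was actually ascertained. For a patient who has gone home, that may be the discharge date. Since early discharge is likely to be related to prognosis, show how many were censored in this way.
- **Control event rate.** State that it is the day-30 Kaplan-Meier estimate, or the proportion among all participants randomized at least 30 days before the data cut, with its confidence interval. State that any sample-size advice rests on that figure.

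The cost is SAP wording and a little more analysis. The safety look is not delayed. The event-rate check may be less precise or come later: the last of the 170 patients reaches day 30 some 23 days after the 7-day trigger (30 − 7).
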